Cigarette and product evaluation	Х	Х	Х		Х	Х		Х	
Carbon Monoxide	Х	Х	Х	Х	Х	Х	Х	Х	
Cotinine		Х	Х	Х	Х	Х	Х	Х	
Ecological momentary assessments	Х	Х	Х	Х	Х	Х	Х	Х	
Adverse health events			Х	Х	Х	Х	Х	Х	

Table 1. Study Assessments

product [if applicable]. The study database will randomize participants, stratified by clinic, gender, and race [White vs. Non-White], to enhance scientific rigor and reproducibility. Participants will use their alternative products as they would like for one week to become comfortable with the product¹¹⁴. Participants will also provide a urine sample for cotinine assessment and be given eight study patches to use during Switch Week 1 when all participants will be asked to abstain from using their own cigarettes for the week. At Visit 2, all participants will complete assessments, provide a breath sample for CO assessment and a urine sample for cotinine assessment, receive feedback on their compliance with the smartphone assessments. All participants will then attend a mid-Switch Week visit (Visit 3) and an end-of-Switch Week visit (Visit 4) to assess biomarkers (a breath sample for CO assessment and a urine sample for cotinine). At Visit 4, the end of Switch Week 1, all participants will be told that they can smoke as usual for a week. In addition, all participants will be given the other type of patch (active or placebo) and asked to use these patches at the start of Switch Week 2 (Visit 5) when they are asked to abstain from smoking their own cigarettes for a week. As during the prior Switch Week, all participants will attend visits mid-week and at the end of the week to assess biomarkers (Visits 6 and 7). To enhance reproducibility, we will attempt to schedule appointments at the same time of day (i.e., within a 2-hour window) for each participant so that there is consistent time for product use prior to providing the biological samples across study visits. We opted to use a 7-day switching period to provide a stronger test of the ability of these alternative products to substitute for cigarettes than in our prior study⁵⁰ (A.5.1), but to minimize the retention problems seen in studies with longer switches¹¹². There are also strong theoretical and empirical reasons to suspect that withdrawal and other motivations for cigarette use will be strongest in the first 7 days of switching, and this design will allow sampling of the full range of work/nonwork environments for most participants¹¹⁵. Participants will complete a follow-up assessment call at 3 months. The baseline visit will last 2 hours, but subsequent visits will last <30 minutes.

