We will use an exhaled CO < 6 ppm to indicate recent abstinence from combustible products, based on Perkins' cut-off of <5 ppm using a Breathco CO monitor¹³⁹, which is similar to the Vitalograph brand, and produces CO values approximately 1-2 ppm lower than the Bedfont Smokerlyzer monitors¹⁴⁰ we will use in this research. Cotinine will be assessed using NicAlert strips, an immunochromatographic assay that uses monoclonal antibody-coated gold particles and a series of avidity traps to quantify cotinine level. We will use the <100 ng/ml cut-off for non-tobacco users recommended by NicAlert to indicate abstinence from nicotine. The NicAlert strips have 91% specificity and 92% sensitivity at this cut-off compared to liquid chromatography-mass spectrometry¹⁴¹. To maintain the patch double-blind and enhance the scientific rigor, study staff who have no contact with participants will conduct the urine assays.

Ecological momentary assessments. We will assess cigarette and alternative product use in real time in the real-world environment (i.e., ecological momentary assessment [EMA]) using a smartphone app we have used in our prior research. Participants can choose to have the app downloaded on their own smartphone or they will be given a smartphone at the Orientation visit and will be trained to press a button marked "Cigarette" every time they start a new cigarette and to press one marked "JUUL" or "Study Cigarette" every time they use a VLNC or e-cig (which they will be able to use after Visit 1). Participants randomized to receive no alternative product will just record their cigarette use. Daily, each time someone presses a product use button (either to say they used the alternative product or to say they smoked their

"Understanding the real-world impact of the use of three alternate nicotine-delivery products on combustible cigarette use" PI: [name]; UW-CTRI Grant: R01CA239309

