own cigarette), there is approximately a 30% chance a more comprehensive assessment (3) minutes) will be triggered that will include: 1) time since prior use of cigarette/alternative product), 2) use context (e.g., smoking prohibited, others vaping/smoking, home, work), activity, and withdrawal symptoms and affect prior to use, and 3) individual items from the mCES that tap potential mechanisms (e.g., product satisfaction, psychological reward, aversion, enjoyment of respiratory tract sensations, and craving reduction). The comprehensive assessments will be specific for each type of use event (i.e., cigarettes, VLNCs, and e-cigs). All participants will complete an evening assessment prior to going to bed. Evening reports (5 minutes) will assess: affect, withdrawal, use of cigarettes and alternative products, overall satisfaction with cigarettes/alternative products, use of patch during Switch Weeks, smoking cues, stressors, and pleasure in daily activities. Participants will spend less than 25 minutes each day recording use events and answering questions, eliminating the problems of recall bias or participants prefilling or back-filling a traditional daily diary. This approach is more rigorous than relying on participants to document their use of non-experimental products using a paper and pencil log¹⁴². We have conducted numerous EMA studies and will use the strategies that have been successful in our earlier work: training in assessments, ability to briefly postpone assessments, use of counters, etc.^{50,86,143}. This frequency of assessment is of moderate intensity relative to protocols used in our prior work⁸⁶.

Follow-up assessment call. Three months after Visit 1, participants will complete a brief follow-up assessment call to assess current smoking, use of any alternative products, motivation and self-efficacy for smoking cessation, risk perceptions, and future plans to use VLNCs, e-cigs, and patches.

Participants who are interested in quitting smoking after Visit 7 will be offered the Wisconsin Tobacco Quit Line toll-free number? ([name]) and the phone number(s) for smoking cessation studies being conducted at our Center.

Alternative Products and the Nicotine Patch

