The primary aim of this research is to examine the ability of VLNCs and e-cigs to substitute for smokers' usual cigarettes compared to each other and to no alternative product use (Product between-subjects effects) and whether these effects are influenced by steadystate nicotine (Patch within-subjects factor; active vs. placebo patch). The primary analysis model will consist of a mixed analysis of variance (ANOVA) with three levels of the Product between-subjects factor (VLNCs, e-cigs, no alternative product) and two levels of the Patch within-subjects factor (active nicotine patch, placebo patch). To address the primary aim, we will explore statistically significant main or interaction effects in the mixed ANOVA by means of unadjusted simple main effects, interaction contrasts, and pairwise comparisons^{156,157}. Specifically, we will examine the main effect of Product to evaluate the hypothesis that participants who do not have an alternative product will report smoking significantly more of their own cigarettes during the Switch Weeks compared to those who have VLNCs or e-cigs. We will also conduct a pairwise comparison to explore whether there is a significant difference in the number of conventional cigarettes smoked in the VLNC vs. e-cig conditions. We will use the main effect of Patch (active vs. placebo) to evaluate the hypothesis that participants will report smoking fewer of their own cigarettes during Switch Weeks when they receive active nicotine patches compared to placebo patches. We will also test the Patch x Product interaction, with follow-up pairwise comparisons, to examine whether steady-state nicotine produces a differential effect on the number of conventional cigarettes smoked, based on which alternative product a participant was assigned to receive.

The primary outcome is the number of conventional cigarettes smoked during each Switch Week. Based on the literature and our own research, it is possible this outcome will not be normally distributed (i.e., a substantive proportion of participants may smoke no conventional cigarettes during a Switch Week). Therefore, prior to conducting main analyses, we will examine the distributional characteristics of the primary outcome to determine if a transformation is needed (e.g., if the distribution substantially deviates from a normal distribution).

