The secondary outcome is number of VLNCs or JUUL pods used during each switch week. This research will also examine the main effects for Product and Patch and the Product X Patch interaction effect on other exploratory outcomes: 1) the proportion of conventional cigarettes replaced; 2) the use of alternative tobacco products; 3) use contexts; and 4) potential mechanisms such as rewarding value of the alternative products and conventional cigarettes, alleviation of withdrawal symptoms, and taste. We will also explore the impact of person factors (e.g., sex, education, psychiatric comorbidity, dependence) and risk perceptions on the primary, secondary, and exploratory outcomes. We will include these variables as covariates in the analyses, and we will include covariate interaction terms with the between- and within-subjects factors (e.g., sex x Product; sex x Product x Patch) to determine whether these individual difference variables moderate the ability of the alternative products to substitute for conventional cigarettes. To examine use contexts and putative mechanisms driving alternative product use and substitution for conventional cigarettes, we will use the daily EMA data from the evening reports as well as data from the quasi-random daily assessments that will be collected during the Switch Weeks as described above as the exploratory outcome variables. One set of analyses will test summary versions of the outcomes (e.g., means or counts across the Switch Weeks); another set of more fine-grained analyses will preserve the intensive longitudinal data (ILD) aspect of the EMA data collected during each of the 7 days of the Switch Weeks. For the summary versions of the outcomes, the alternative product use outcome will consist of the mean alternative product use events per day reported during the Switch Weeks and the context

"Understanding the real-world impact of the use of three alternate nicotine-delivery products on combustible cigarette use" PI: [name]; UW-CTRI Grant: R01CA239309

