and mechanisms variables will be based on means across the 7 days of the Switch Weeks. For these summary outcomes, we will use statistical models similar to the analyses described above for the primary outcome. For the ILD outcomes, we will create one set of outcomes based on the evening report that assesses experiences across the full day and another set based on the 3 quasi-random comprehensive assessments that occur during the day. For the ILD versions of the outcomes, we will use conditional growth curve models that permit slope and intercept parameters to be evaluated across the 7 days of the Switch Weeks as a function of group; these models also permit examination of other forms of change over time (e.g., linear, quadratic, cubic). We will explore two main approaches to growth curve modeling: a multilevel modeling (MLM) approach¹⁵⁸ and a structural equation modeling (SEM) approach¹⁵⁹. Although similar, each of these modeling approaches has advantages and disadvantages¹⁶⁰ that we will exploit in exploratory analyses. While we are not powered to detect mediation due to funding limitations, we will conduct exploratory mediation analyses to provide information for future research on whether these mechanisms mediate the effects of alternative product use on the use of conventional cigarettes.

Power for Primary Aim Hypotheses

With attrition-adjusted n=54 per group for a between-subjects pairwise comparison, the study is powered to detect a difference of 3.3 cigarettes (SD=6); a corresponding within-subjects pairwise comparison (SD=6, correlation=0.5) is powered to detect a difference of 2.8 cigarettes. Thus, we feel that a total N=225 provides adequate power to detect predicted effects.

Protection of Human Subjects

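### One exploratory outcome set presumes three quasi-random assessments a day, but the only trigger described is a product-use press, so any withdrawal or affect test from it would be conditional on use

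*Combined protocol and SAP*

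**What the plan says.** The Analytic Plan proposes to test "main effects for Product and Patch and the Product X Patch interaction effect on other exploratory outcomes". Relief of withdrawal is among the mechanisms it lists there. To study use contexts and mechanisms it names two data sources from the Switch Weeks: the evening reports and quasi-random daily assessments, for which it points back to the earlier description. For the intensive longitudinal analyses it plans one outcome set from the evening report and "another set based on the 3 quasi-random comprehensive assessments that occur during the day". Growth curves over the seven days are then compared by group. The plan does not list which variables enter the second set.

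The earlier description is under Ecological momentary assessments. Each time a participant presses a button to record a product use, "there is approximately a 30% chance a more comprehensive assessment" follows. Its content includes use context, "withdrawal symptoms and affect prior to use", and product ratings. That section adds: "Participants randomized to receive no alternative product will just record their cigarette use". It also describes an evening report, completed by every participant, that covers affect and withdrawal.

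Under Study Visits and Phone Contacts, during the Switch Week "all participants will be asked to abstain from using their own cigarettes for the week". Under Visit assessments, the PANAS (affect), WSWS (withdrawal) and QSU-Brief (craving) are completed at each visit.

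**The concern.** The analysis presumes a fixed number of assessments a day at times that look unrelated to use. The data collection described yields a variable number, and only at moments of use. For use contexts and product ratings that is the natural sampling scheme, since they have no meaning without a use event. For withdrawal and affect it is not, because these states exist whether or not the participant smokes or vapes.

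Use is also something the randomised factors are expected to change. The plan expects own-cigarette smoking to be highest without an alternative product, and that "participants will report smoking fewer of their own cigarettes during Switch Weeks when they receive active nicotine patches". A test of momentary withdrawal by Product or Patch in the triggered set would thus compare records selected on a post-randomisation outcome. A difference could reflect who used and when, rather than an effect of the product or of nicotine. At stake is the reading of exploratory mechanism results, on a topic that the Secondary Aims name.

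**Working it through.** **Inputs.** Trigger probability about 0.30 per press (Ecological momentary assessments). Stated number of assessments: 3 a day (Analytic Plan). Presses per day in the Switch Weeks are not given, so a range is shown. Presses are treated as independent.

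**Does the described trigger give 3 a day?** With k presses, the count is Binomial(k, 0.30): mean 0.30k, and P(none) = 0.70^k. A mean of 3 needs k = 3 / 0.30 = 10.

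| Presses in a day | Mean assessments | P(none) | P(at least 3) |
|---|---|---|---|
| 0 | 0 | 1.00 | 0 |
| 1 | 0.3 | 0.70 | 0 |
| 2 | 0.6 | 0.49 | 0 |
| 5 | 1.5 | 0.17 | 0.16 |
| 10 | 3.0 | 0.03 | 0.62 |
| 20 | 6.0 | 0.001 | 0.96 |

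Even at 10 presses, P(exactly 3) = 120 × 0.3^3 × 0.7^7 = 0.27. The stated 3 is not reproduced as a fixed number.

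**Who has no record in a whole Switch Week?** With m presses in the week, P(no record) = 0.7^m:

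- m = 0: 100%
- m = 1: 70%
- m = 3: 0.343, or 34%
- m = 7: 0.082, or 8%

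**How does this fall across arms?** A no-product participant has only the own-cigarette button. One who abstains fully has m = 0 and supplies nothing. A VLNC or e-cig participant who switches fully can still supply records through alternative-product presses. The plan itself anticipates that "a substantive proportion of participants may smoke no conventional cigarettes during a Switch Week", so the empty case is not remote.

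**How does it fall across patch weeks?** A no-product participant who abstains in one Switch Week but smokes in the other can have triggered records only in the week with smoking. No within-person patch contrast can be formed from that person's triggered data.

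**Is there another source of daytime prompts?** None is described. The payment terms, under Promoting Continued Experimental Participation, refer to completing a percentage of prompts but give no schedule for them.

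**The case against.** **The wording may be loose rather than wrong.** A random 30% draw of use events can fairly be called quasi-random, and 3 could be a rough average at 10 presses a day, a cap, or text from another schedule. The documents do not say which, so the request to clarify stands.

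**The problematic test is not shown to be planned.** The Analytic Plan names the evening reports and the triggered data together, and does not assign withdrawal or affect specifically to the triggered set. That is correct, and the point is worded conditionally for this reason. But withdrawal relief is listed for Product and Patch tests, this set is named as a data source, and the triggered form carries withdrawal and affect items. Nothing in the plan rules the test out.

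**The constructs are already covered.** The evening report gives withdrawal and affect for all participants, and the visit scales add to it. This stands. It limits the harm and is what makes the fix cheap.

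**A stronger reading is tempting.** A reader might infer that the low-use arm or week would look worse, because its few uses occur when withdrawal is high, and might try to put a size on that. The documents do not support this. They give neither press rates nor the relation between withdrawal and use, and the answer depends on the model. Suppose withdrawal W is standard normal and the use rate is c × exp(bW), with the same b in each arm. Then the mean of W at moments of use is b whatever c is, because c cancels, so very different use rates give no between-arm difference. Other models, different slopes by arm, or the loss of whole participants could produce a difference. Neither size nor direction follows from the plan.

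**Conclusion.** The mismatch is real. The plan relies on three assessments a day that its described trigger does not deliver, and that trigger yields nothing from a no-product participant who abstains. Any Product or Patch test of withdrawal or affect drawn from this set would be conditional on use after randomisation and would exclude those participants. The counts rest on the stated 30% and on independence between presses. The absence of records from abstainers needs no assumption beyond the described trigger being the only one.

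This is a minor point. The primary outcome, the secondary outcome and the power statement are unaffected, as are the evening-report set and the visit scales. Confidence is high for the contradiction in the text and for the exclusion of abstainers; no claim is made about the size or direction of bias.

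**What to change.** 1. Reconcile the Analytic Plan with the Ecological momentary assessments section. Either correct the reference to three quasi-random assessments, or describe prompts that do not depend on use if they exist. Say whether 3 is a mean, a target or a cap, and list the variables taken from this set.
2. If the assessments are only event-triggered, base Product and Patch tests of withdrawal and affect on the evening report and on the WSWS and PANAS at visits, and tests of craving on the QSU-Brief.
3. Keep the triggered set for use contexts and product ratings, and label those results, including active versus placebo week, as conditional on use.
4. Report by arm and patch week the number of triggered assessments and the number of participants with none.

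The cost is some wording and one descriptive table, with no new data collection. The downside is coarser timing: withdrawal and affect tests would rest on one evening record a day plus the visits, and craving tests on the visits alone.

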This mixed design study (within-subjects Patch factor: active nicotine and placebo patch; between-subjects Product factor: VLNC, e-cigarette, or no alternative product) will allow us to address key questions identified in the RFA-OD-18-002. Specifically, we will assess the potential "impact of novel and/or potential modified risk tobacco products on tobacco behavior" and provide data that estimates the real-world impact of potential regulatory actions. To address these questions, this research will focus on the following aims:

Primary Aim: Examine the ability of VLNCs and e-cigarettes to substitute for smokers' usual cigarettes compared to each other and to no alternative product use in real-world settings (between-subjects effects) and whether these effects are influenced by active nicotine replacement (interaction with within-subject factor).

Secondary Aims: Examine the main effects of VLNCs and e-cigarette use compared to each other and to no product use as well as their interaction with active vs. placebo patch on: 1) the use of study alternative products, and 2) mechanisms underlying product use (e.g.,

"Understanding the real-world impact of the use of three alternate nicotine-delivery products on combustible cigarette use" PI: [name]; UW-CTRI Grant: R01CA239309

withdrawal alleviation, taste, satisfaction). We will also explore the contexts that promote or inhibit switching from conventional cigarettes to alternative products and whether participants' risk perceptions and key person factors (e.g., gender, race, education, psychiatric comorbidity) influence switching, alternative product use, and the potential mechanisms that drive such use behavior.

Recruitment and Study Entry

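### The within-subjects detectable difference (2.8) does not follow from the inputs that give the between-subjects one (3.3), and the primary-aim interaction has no power figure

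*Combined protocol and SAP*

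**What the plan says.** All references are to the combined protocol and SAP. The section Power for Primary Aim Hypotheses contains two figures and a conclusion:

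- Between subjects: "With attrition-adjusted n=54 per group for a between-subjects pairwise comparison, the study is powered to detect a difference of 3.3 cigarettes (SD=6").
- Within subjects: "a corresponding within-subjects pairwise comparison (SD=6, correlation=0.5) is powered to detect a difference of 2.8 cigarettes".
- Conclusion: "Thus, we feel that a total N=225 provides adequate power to detect predicted effects".

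It states no alpha, sidedness or target power, and it gives no separate n for the within-subjects comparison.

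The Primary Aim has two parts: how well the products substitute for usual cigarettes, and "whether these effects are influenced by active nicotine replacement (interaction with within-subject factor"). The Analytic Plan carries the second part into the primary mixed ANOVA: "We will also test the Patch x Product interaction, with follow-up pairwise comparisons". It also says that follow-up comparisons are unadjusted, and it defines the outcome as a weekly count: "The primary outcome is the number of conventional cigarettes smoked during each Switch Week".

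**The concern.** With the same SD, the same n per arm and a correlation of 0.5, a paired comparison should detect a difference smaller than the two-sample one by a factor of about 1.4. The stated figures differ by a factor of only 1.18. Either 2.8 is wrong, or it describes another comparison, or one of its inputs is not the one printed.

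Which of these is true matters beyond the patch comparison, because the within-person correlation also sets the sensitivity of the interaction test. That test answers half of the primary aim, yet the paragraph that declares the sample size adequate gives no figure for it. If the interaction came out null, a reader could not tell from the plan what size of interaction the trial was able to detect.

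The SD of 6 also has no time unit. A per-day scale is likely but is not stated, so the detectable differences cannot be matched to the weekly count.

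**Working it through.** **Inputs from the plan.** n = 54 per arm, SD = 6 and correlation r = 0.5 (Power for Primary Aim Hypotheses).

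**Assumptions.** Two-sided alpha 0.05 and 80% power. The within-subjects comparison uses 54 participants, because the plan calls it the counterpart of the between-subjects one. Detectable differences come from the noncentral t distribution.

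**1. Between-subjects figure.**
SE = 6 × √(2/54) = 1.155, with 106 df.
Detectable difference at 80% power: 3.26. Power at 3.3: 80.8%.
The plan's 3.3 reproduces as the usual 80% figure.

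**2. Within-subjects figure.**
SD of the paired difference = 6 × √(2 × (1 − 0.5)) = 6.
SE = 6/√54 = 0.816, with 53 df.
Detectable difference at 80% power: 2.33; at 90% power: 2.70. Power at 2.8: 92.0%.
The plan's 2.8 does not reproduce.

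**3. Could the unstated alpha and power explain it?** With n, SD, alpha and power in common, the ratio of the two figures is approximately 1/√(1 − r) = √2 = 1.414. With the t distribution it is slightly lower:

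| Two-sided alpha | Between/within ratio at 80% power |
|---|---|
| 0.10 | 1.405 |
| 0.05 | 1.401 |
| 0.025 | 1.397 |
| 0.0167 | 1.395 |
| 0.01 | 1.392 |

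Raising power to 95% changes these by at most 0.001. The stated ratio is 3.3/2.8 = 1.18. Allowing for rounding, it lies between 3.25/2.85 = 1.14 and 3.35/2.75 = 1.22. No shared setting reaches it.

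**4. What would give 2.8?** Each line is a possibility; the documents do not say which applies.

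- A Product contrast between two arms on the mean of both Switch Weeks: SD = 6 × √((1 + 0.5)/2) = 5.196, detectable difference 2.83. Here r = 0.5 stands and the label is wrong.
- The paired comparison with n = 54 and r ≈ 0.28 (detectable difference 2.80).
- The paired comparison with about 38 participants instead of 54.
- The paired comparison with alpha near 0.01, or with about 92% power, while the between-subjects figure keeps 0.05 and 80%.

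Pooling all three arms (3 × 54 = 162) gives 1.33, which is further from 2.8.

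**5. The missing interaction figure.** The contrast is the patch effect in one arm minus the patch effect in another:
SE = 6 × √(2(1 − r)) × √(2/54).

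| r | Detectable interaction contrast, 80% power |
|---|---|
| 0.28 | 3.92 |
| 0.3 | 3.86 |
| 0.5 | 3.26 |
| 0.7 | 2.53 |

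For the overall test of the interaction at r = 0.5 (F with 2 and 159 df), power reaches 80% in either of two patterns. In one, the patch effect is 3.1 larger in one arm than in the other two. In the other, the three arms are evenly spaced over a range of 3.6.

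**The case against.** The strongest reply is that the sentence is literally true. The plan says the comparison is powered to detect 2.8 and does not call 2.8 the minimum; with 92% power, 2.8 is detectable. The inconsistency appears only if both figures share alpha, power and n, and the plan does not say so outright. That is correct, but shared settings are the natural reading. The plan presents the second figure as the counterpart of the first, its follow-up comparisons are unadjusted, and no separate alpha, power or n is given.

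A second reply is that nothing in the trial's conduct depends on this. The slip is conservative. The Patch hypothesis is tested as a main effect over all arms, where 162 participants detect about 1.33. This stands, and it is why the point is a correction to the text and not a challenge to the sample size.

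Third, r = 0.28 appears nowhere in the plan and was solved backwards from 2.8. That also stands: the interaction figure of 3.9 is conditional on one explanation, and the mislabelled-contrast explanation leaves it at 3.3. Likewise, the plan predicts no interaction size, so power quoted for any particular interaction would refer to no planned effect.

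Fourth, only the Product and Patch main effects are worded as directional hypotheses, so the statement about predicted effects may be meant for them alone. That is a possible reading. However, the section is headed as covering the primary aim, which includes the interaction, and a reader should not have to guess.

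**Conclusion.** The concern holds. As labelled, 2.8 is not the counterpart of 3.3: on the stated n, SD and correlation it should be about 2.3 at two-sided 0.05 and 80% power. The mismatch itself does not depend on those two assumed values; it rests on the two comparisons sharing alpha, power and 54 participants per arm. The error does not show the patch comparison to be underpowered. Its source cannot be determined from the documents.

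For the interaction, adequate power is not shown, which is different from disproved. The detectable two-arm contrast is about 3.3 if the correlation of 0.5 is right, and about 3.9 if 2.8 came from a correlation near 0.28. The missing alpha, power, time unit and interaction figure are gaps in reporting; the error proper is the within-subjects figure. This should be fixed, but it does not threaten the design.

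**What to change.** The sponsor should retrieve the source calculation and rewrite the power paragraph:

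1. State alpha, sidedness, target power, the n for each comparison, and whether SD = 6 is per day or per Switch Week.
2. According to what the calculation shows, correct the within-subjects figure to about 2.3, or relabel 2.8 as the Product contrast averaged over both weeks, or correct the correlation. If 2.8 used a different alpha, power or n, state that setting.
3. Add the detectable difference for the Patch x Product contrast: about 3.3 at r = 0.5, or the value for the confirmed correlation.
4. Limit the statement of adequate power to the Product and Patch comparisons, and say that the interaction is powered only for differences of about that size or larger.

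The cost is one paragraph of text after a check of the calculation. The sample size and the definition of the primary outcome stay as they are. The one drawback for the sponsor is that the plan must admit limited sensitivity for the interaction.
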